## 4. Statistical Analyses

### 4.1 General Considerations

Statistical analyses will be performed using SAS release 9.4 or higher (SAS Institute Inc., Cary, North Carolina, US).

All variables will be analyzed descriptively with appropriate statistical methods: categorical variables by frequency tables (absolute and relative frequencies) and metric (or continuous) variables by sample statistics (i.e. mean, standard deviation [SD], minimum, median, quartiles, and maximum). The number of data available and missing data will be calculated

for metric data. Continuous variables will be described by absolute value and as change from baseline per analysis time point, if applicable.

All data will be presented in the participant data listing as they are recorded on the electronic case report form (eCRF), eDiary and Interactive Voice/Web Response System (IxRS), i.e. partially missing data will appear as such.

The primary analysis will be performed after the database lock after Last Participant Last Visit.

The mITT set will be used to analyze endpoints related to the effectiveness objectives and the safety analysis set will be used to analyze the endpoints and assessments related to safety. Data will be pooled across study sites for all reporting of participant characteristics, primary, secondary, and safety endpoints.

Analysis will be presented overall for the combined risk score groups. Some tables will be stratified by the risk score-selected dosing regimen. Analysis of risk score-selected dosing regimen will include the entire treatment period. The first 8 weeks on study will not be presented separately. Safety listings will include assigned dosing regimen, based on risk score, and actual current dosing regimen at start of AE or time of assessment. Safety summaries will be presented only overall, for the combined risk score groups.

Subgroup analysis of study endpoints and safety events by history of FVIII inhibitors will be presented only if the mITT set includes at least 5 participants in each category, with and without history of FVIII inhibitors.

In general, missing clinical outcomes as well as missing assessments of PRO summary scores collected in this study will not be imputed. Missing exposure and AE/concomitant medication start/end date will be imputed based on a worst case scenario. For calculation of intra-individual change from pre-study value or baseline: No missing baseline ABR or frequency of administration is expected among participants who meet study enrollment criteria, as these are required to calculate total risk score.

Visit 2 is considered baseline, when the participants risk score and resulting regimen scheme will be determined (refer to [section 1.2.2](#)).

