#### **9.4.4 Safety Analyses**

All safety analyses will be performed on the Safety Population and will be presented overall and stratified by FVIII inhibitor history.

Adverse events will be reported using the latest version of the Medical Dictionary for Regulatory Affairs (MedDRA).

Individual listings of AEs will be provided which will include any information on history of FVIII inhibitors.

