**Table 3: Analysis Sets**

Participant Analysis Set	Description
Enrolled	All participants who signed the ICF
Modified intention-to-treat (mITT) set	All enrolled participants who had received at least 1 dose of study intervention, who have infusions/bleeding data from the diary and CRF available, and who have been followed for a minimum of 4 months.
Safety analysis set	All participants who had received at least 1 dose of study intervention.

Abbreviations: CRF = case report form; ICF = informed consent form.

Final decisions regarding the assignment of participants to analysis sets will be made during the review of study data and documented in the final list of important deviations, validity findings and assignment to analysis set(s).

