### 4.2.2 Main Analytical Approach

The analysis of the primary endpoint will be performed on the mITT population.

The entire study intervention period will be analyzed regardless of the score assigned dosing regimen (i.e. during the first 8 weeks on the study).

The strategy for primary endpoint analysis, including how to deal with participants who switch regimen frequency is listed below:

- A switch to a higher frequency regimen than the one assigned by the score, due to a bleed during study, is considered as non-favorable outcome
- Participants who switch due to other reasons than bleeding events (e.g. personal decision, study compliance issues, or changes in physical activity level) will be censored at the time of regimen change
  - switch after 4 months ( $> 122$  days): participant data will be analyzed until censoring
  - switch prior to 4 months ( $\leq 122$  days): participant data will not be used for analysis, as it is assumed that a shorter duration will not be sufficient to correctly estimate the ABR and would bias the results.

Note: a decrease in regimen per score assignment (during the first 8 weeks) is not considered a switch as discussed above.

Favorable outcome assessed by total ABR and frequency of administration (/month) is evaluated after considering regimen switch events.

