### 4.5 Safety Analyses

All safety analyses will be performed on the safety analysis set. Summary tables will be presented overall and stratified by subgroup of history of FVIII inhibitors.

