- Any AE with causal relationship to protocol-required study procedures with outcome death

If post-treatment AEs occur (i.e., those occurring >7 days after the last infusion of Jivi), these will be presented in an overall summary table and in a summary by primary SOC and PT.

In all AE summary tables, multiple AEs within same category of primary system organ class (SOC) or preferred term (PT) for a participant will be counted only once in that category. In summaries of events with causal relationship a participant with related and unrelated events in any category will be counted for event with causal relationship experienced in that category.

The following summaries of TEAEs will be presented

- TEAEs by primary SOC and PT overall and stratified by FVIII inhibitor history

The following summaries of TEAEs will be presented overall

- Study intervention-related TEAEs by primary SOC and PT
- Study intervention-related TE AESIs (including SAE/AESI) by primary SOC and PT
- Study procedure-related TE AESIs (including SAE/AESI) by primary SOC and PT
- Medical device-related TE AE by primary SOC and PT
- Medical device deficiency
- TEAEs leading to discontinuation of the study intervention by primary SOC and PT
- TE non-serious AEs by primary SOC and PT

The following summaries of TE SAEs will be presented

- TE SAEs by primary SOC and PT
- Study intervention-related TE SAEs by primary SOC and PT
- Study procedure-related TE SAE AESIs by primary SOC and PT
- Medical device-related TE SAE by primary SOC and PT

Individual listings of AEs, SAEs, and AEs leading to discontinuation will be provided with a flag to identify TE status. The individual listings will include any information on history of FVIII inhibitors.

If any death occurs, then summaries and listings of fatal AEs and deaths will be provided.

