#### 4.6.4 Subgroup Analyses

Some selected tables (including the primary endpoint, safety events, study intervention administration, prophylaxis regimen, and PK parameters) will be presented in total and by subgroup of history of FVIII inhibitors for sensitivity purposes. This analysis will be performed only if each subgroup has at least 5 subjects evaluated for the primary endpoint.

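### The safety tables by FVIII-inhibitor history depend on a count that leaves out early withdrawals, although they are tabulated on the safety analysis set and the protocol sets no threshold

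*SAP*

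**What the plan says.** The SAP sets two conditions on the inhibitor-history subgroups, and both cover safety events.

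- SAP 4.1, in a rule that also governs the effectiveness subgroups: "safety events by history of FVIII inhibitors will be presented only if the mITT set includes at least 5 participants in each category".
- SAP 4.6.4, whose list of tables includes safety events: "This analysis will be performed only if each subgroup has at least 5 subjects evaluated for the primary endpoint".

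Elsewhere the plan says the following.

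- SAP 4.1 also states that "the safety analysis set will be used to analyze the endpoints and assessments related to safety". SAP Table 3 defines that set by one dose, with no minimum follow-up. The mITT is limited to participants "who have been followed for a minimum of 4 months".
- SAP 4.2.2 removes one more group from the primary analysis. For participants who change regimen by day 122 for a reason other than bleeding, "participant data will not be used for analysis, as it is assumed that a shorter duration will not be sufficient".
- SAP 4.5: "Summary tables will be presented overall and stratified by subgroup of history of FVIII inhibitors". SAP 4.5.2 lists "TEAEs by primary SOC and PT overall and stratified by FVIII inhibitor history". Protocol 9.4.4 says that safety analyses "will be presented overall and stratified by FVIII inhibitor history". None of the three carries a minimum count.
- SAP 1 and SAP 4.7 report no change from the protocol's analyses. The SAP version history mentions a rule of n≥5 for inhibitor history but does not name the set in which it is counted.

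**The concern.** Whether a safety table is shown should not depend on an outcome that the table reports. Here it can. Protocol 7.1.1 withdraws a participant who discontinues because of inhibitor development. Protocol 7.2 requires withdrawal when an antibody interferes with effective treatment or a bypassing agent is needed. If that happens before month 4, the participant stays in the safety analysis set but leaves the mITT, and so leaves the count that decides whether the table is produced. Any other early withdrawal has the same effect. Under SAP 4.6.4, so does an early non-bleeding regimen switch by someone still on drug.

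The text also conflicts with itself. If either count falls below 5, a programmer cannot follow SAP 4.1, 4.6.4, 4.5, 4.5.2 and Protocol 9.4.4 together.

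What can be lost is the protocol-planned incidence table with a denominator by inhibitor history. Amendment 2 added this stratification to assess how inhibitor history affects safety. Amendment 3 then relaxed entry for the same group, shortening the exclusion for inhibitor evidence from 3 years to 1 year.

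**Working it through.** **The plan's own figure.** The only computed design figure is the Clopper-Pearson interval for 14/20. It reproduces as 45.7% to 88.1%, width 42.4 points. This concern does not depend on it.

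**Who is counted where** (SAP Table 3, 4.1, 4.2.2, 4.6.4):

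| Participant, dosed at least once | Safety set | SAP 4.1 count (mITT) | SAP 4.6.4 count |
|---|---|---|---|
| Followed ≥4 months with diary/CRF data, no early switch | yes | yes | yes |
| Followed ≥4 months, non-bleeding switch by day 122 | yes | yes | no |
| Withdrawn before 4 months | yes | no | no |

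With 5 dosed participants who have an inhibitor history and 1 lost early, the safety set holds 5 and the mITT holds 5 − 1 = 4. The condition fails on the mITT and would pass on the safety set. With 6 dosed, it takes two losses.

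**Probability that the table is dropped, given k dosed with a history.** Let d be the chance that each participant is lost before 4 months, independently. The documents give no such rate, so d = 2%, 5% and 10% are assumptions.

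- k = 5: P = 1 − (1 − d)^5. At 5%: 1 − 0.95^5 = 0.226.
- k = 6: P = 1 − (1 − d)^6 − 6d(1 − d)^5. At 5%: 1 − 0.735 − 0.232 = 0.033.

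| k | d = 2% | d = 5% | d = 10% |
|---|---|---|---|
| 5 | 9.6% | 22.6% | 41.0% |
| 6 | 0.6% | 3.3% | 11.4% |

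For context, the superseded plan of 70 enrolled for about 60 evaluable implies 10/70 = 14.3% not evaluable. That is not a measured early-loss rate. At 14.3% the figures would be 54% (k = 5) and 21% (k = 6).

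**Unconditional share of trials affected.** Let K, the number with a history, be Binomial(N, p), with N = 20 or 25 (SAP 5) and p assumed. The quantity is the probability that K ≥ 5 and N − K ≥ 5 among those dosed, but fewer than 5 remain in at least one group after early losses.

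| p | N | Threshold met in safety set | Table lost, d = 2% | d = 5% | d = 10% |
|---|---|---|---|---|---|
| 10% | 20 | 4% | 0.3% | 0.8% | 1.4% |
| 10% | 25 | 10% | 0.6% | 1.5% | 2.9% |
| 20% | 20 | 37% | 1.7% | 4.3% | 8.5% |
| 20% | 25 | 58% | 2.0% | 5.0% | 10.2% |
| 30% | 20 | 76% | 1.8% | 4.7% | 10.0% |
| 30% | 25 | 91% | 1.1% | 2.9% | 6.4% |

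At 10% prevalence the table would usually be absent under either count. These figures use the mITT count in SAP 4.1. The count in SAP 4.6.4 also drops early non-bleeding switchers, so it can only fail as often or more often.

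**A contrast within the SAP.** For disposition by inhibitor history, SAP 4.6.1 requires at least 5 per group with no mITT condition.

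**The case against.** The strongest reply is that little is lost, and rarely.

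- **The inhibitor route is remote.** Participants have at least 150 exposure days and no current inhibitor. Protocol 2.3 reports no new or confirmed inhibitors in the clinical studies of Jivi. After screening, testing is done only on suspicion. Discontinuation for a high titer is only to be considered, and low-titer inhibitors need not lead to withdrawal. The 2–10% loss rates above are generic, and no probability is attached to the safety-event route.
- **The information survives.** AE listings carry inhibitor history (SAP 4.5.2). Confirmed inhibitors are counted overall (SAP 4.5.3). Disposition with discontinuation reasons is given by history, subject to its own rule of 5 (SAP 4.6.1). SAP 4.6.2 tabulates inhibitor history in the safety analysis set, so the denominators are reported. With about 5 participants, the stratified rates could be rebuilt by hand.
- **The headline case is narrow.** Exactly 5 with a history occurs in about 3% to 20% of trials over the assumed prevalences.
- **The rule is disclosed and sensible.** A general section can be read as governing later ones, and the version history gives the reduced sample size as the reason. Protocol 9.4.1 describes these subgroup tables as serving sensitivity purposes. A single count also keeps the effectiveness and safety subgroups matched.

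All of this limits the importance, and a minimum count is reasonable with 20–25 participants. It does not remove the fault. The rule is counted in a set other than the one tabulated, two unequal counts apply to the same tables, and three other sections promise those tables without condition.

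**Conclusion.** The concern holds. Followed as written, SAP 4.1 and 4.6.4 can drop a safety table planned in Protocol 9.4.4 because a participant left early, even though that participant belongs to the set being tabulated. The size depends on how many participants with a history are dosed: about 10% to 41% with exactly 5, 0.6% to 11% with 6, and 0.3% to about 10% averaged over enrolment. These figures assume independent losses of 2% to 10% and a prevalence of inhibitor history of 10% to 30%; the documents supply neither.

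The consequence is modest. The study is descriptive, no primary or overall safety result changes, and the events remain in the listings and overall tables. The conflict in the text is certain and should be corrected.

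**What to change.** 1. In SAP 4.1 and 4.6.4, limit the mITT or primary-endpoint count to effectiveness tables.
2. For safety tables, write: *Summaries of safety events by history of FVIII inhibitors will be presented if the safety analysis set includes at least 5 participants in each category.*
3. Refer to that sentence in SAP 4.5, so that the stratification there and in 4.5.2 is no longer unconditional.
4. Record the remaining threshold in SAP 4.7 as a change from Protocol 9.4.4, and correct the statement in SAP 1.

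The cost is SAP wording. No new data are needed. The stratified tables are already planned, so new shells should not be needed, although the shells sit in a separate document and should be checked. The downsides are small cells in some safety tables and, occasionally, a safety table by inhibitor history with no matching effectiveness table.

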#### **4.1.1 Data Rules**

##### **4.1.1.1 Annualized bleed rate (ABR)**

Pre-study ABR is reported in History of Hemophilia eCRF as 'ABR during period of stable SHL treatment'.

The ABR response is calculated over the entire intervention period:

- Intervention period (days) = (1 + Visit 6/EOS date – Visit 2 date)

The ABR is calculated using the number of bleed events reported to the eDiary. Types of bleed event and counting of bleeds are described in the section below.

The ABR for each type of bleed will be calculated as:

- $ABR = 365.25 \times \# \text{ of bleed events} / \text{Intervention period (days)}$ 
  - ABR will be rounded to 2 decimal places

Improved, similar, or worsening ABR will be assessed by comparison to pre-study ABR:

$$ABR_{post} - ABR_{pre} = \begin{cases} \geq 1 & worsening \\ (-1, 1) & similar \\ \leq -1 & improved \end{cases}$$

#### 4.1.1.2 Counting of Bleeds

- 'Treated bleeds' will include all treated bleeds (=all treated spontaneous and treated trauma bleeds).
- 'All bleeds' will include all bleeds, regardless of treated or untreated.
- A bleed will be counted as treated bleed if either the flag variable from the diary indicates that the bleed was treated or there is a matching infusion for this bleed.

##### 24-hour rule:

All bleeds that occur during the same calendar day will be considered as one bleed. As a bleed event may be in more than one category, priority will be determined according to the following order:

- spontaneous bleed
- joint bleed
- treated bleed
- earliest bleed

The analyzed bleed will be the one with the highest priority. It will be classified by the following derived characteristics:

- combination of all types and locations
- highest treated status (i.e. treated if at least one bleed on that day is treated)

All other bleeds on the same calendar day will not be considered for analysis but only listed in section 16.

##### 72-hour rule:

A spontaneous joint or spontaneous muscle bleed will not be counted if it occurs within 72 hours of a bleed (or infusion for that bleed) at the same site. For a spontaneous bleed to be affected by this rule, all sites listed for the bleed must also be specified in the previous bleeds during a 72-hour time frame. Infusions for such bleeds will be considered to be follow-up infusions. If the current and previous bleeds are both skin/mucosa bleeds, this rule does not apply. The rule operates with date/time and bleed locations adjusted by 24-hour rule. Bleeds eliminated by 24-hour rule are not considered.

#### 4.1.1.3 Joint Bleeds and Target Joints

Target joints will be identified at baseline in the eCRF. Participants will identify the affected joint (site) of any joint bleed during the study in the eDiary. The record of bleed events at each site of each participant will be tracked. The count of joint bleed events for a participant will include all sites and each event at each site that is at least 72 hours after any previous bleed at that site or at least 72 hours after a treatment for a previous bleed at that site.

**Target joints (modified ISTH definition):**

A **pre-existing** target joint is a joint that was reported to be a target joint at start of the study.

A **new** target joint is defined as a joint that was not reported as pre-existing target joint but showed at least 3 spontaneous bleeds during the study (6-month treatment period).

A **resolved** target joint is a previous target joint with  $\leq 1$  spontaneous bleeds during the last 6 months. Due to study design, this definition differs and is pro-rated from the current ISTH definition for resolution of target joints, where 12 months are considered to count for  $\leq 2$  spontaneous bleeds in a joint.

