#### **4.1.2 Treatment**

All participants will receive treatment for a total of 6 months, dispensed using the study IxRS. The total duration of the study will be approximately 7.5 months (including screening, treatment, and safety follow-up period). During the study, all participants will receive treatment with Jivi as prophylaxis and for treatment of bleeds, if they occur. All participants will start with a Jivi dosing regimen of 2x/week (40 IU/kg/dose) for 1 month. Participants will then continue in 1 of 3 treatment regimens assigned according to pre-calculated baseline risk score.

The details about duration and recommended dose regimen of study participation are presented in [Table 4-3](#).

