### **8.2.3 Joint Status Assessment**

A joint status assessment (including target joints) will be recorded at baseline and EOS using the ISTH criteria. A target joint is defined as one having 3 or more spontaneous bleeds into a single joint within a consecutive 6-month period. Where there have been  $\leq 2$  bleeds into the joint within a consecutive 12-month period the joint is no longer considered a target joint (Blanchette et al., 2014).

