## 1. Introduction

Study 21924 (PREDICT) is a multicenter, open-label, single arm, prospective study that aims to assess a new risk score approach utilizing the best known phenotypic and biologic variables to select the most appropriate prophylaxis regimen for reaching a favorable outcome when switching from standard half-life (SHL) human coagulation factor VIII (FVIII) treatment to Jivi. Participants will be  $\geq 12$  years of age with congenital hemophilia A who have a documented history of at least 150 EDs with any FVIII product. All participants will have received prophylaxis with any licensed SHL FVIII product with a stable dosing regimen.

This SAP does not address pharmacokinetic (PK) calculations of parameters derived using the Web-Accessible Population Pharmacokinetic Service Hemophilia (WAPPS-Hemo) system nor medical resource utilization and health economics outcomes that may be collected by data linkage using de-identified data of participants who consent to participate in tokenization.

The SAP describes the final analysis of the study. Table, figure and listing specifications including table mock shells are contained in a separate document.

There are no changes to the analyses described in the protocol.

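### SAP 4.1.1.3 counts only spontaneous bleeds when it calls a target joint resolved; protocol 8.2.3 sets no such limit, and the SAP does not list this as a change

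*SAP*

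**What the plan says.** Protocol 8.2.3 has separate rules for gaining and losing target-joint status. For gaining it: "A target joint is defined as one having 3 or more spontaneous bleeds into a single joint within a consecutive 6-month period". For losing it, the sentence sets a limit of 2 and continues: "bleeds into the joint within a consecutive 12-month period the joint is no longer considered a target joint". The word spontaneous appears in the first rule and not in the second.

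SAP 4.1.1.3, under the heading for its modified ISTH definition, resolves a joint at no more than 1 "spontaneous bleeds during the last 6 months. Due to study design, this definition differs and is pro-rated from the current ISTH definition". It goes on to describe the source rule "for resolution of target joints, where 12 months are considered to count for" no more than 2 spontaneous bleeds. A new target joint needs at least 3 "spontaneous bleeds during the study (6-month treatment period"), which is the protocol's onset rule unchanged. The end-of-study number is pre-existing plus new minus resolved joints.

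SAP section 1 states: "There are no changes to the analyses described in the protocol". SAP 4.7 (Changes to Protocol-planned Analyses) is marked not applicable. In both documents the secondary objective is target joint status per ISTH guidelines. SAP 4.3.2 analyses it in the mITT set, which takes participants "who have been followed for a minimum of 4 months".

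**The concern.** The SAP makes two changes to the protocol's resolution rule and explains only one. The shorter window is stated and attributed to the study design. The bleed type also changes, from bleeds into the joint to spontaneous bleeds. That change is visible in the rule, but because the SAP describes the source rule as already limited to spontaneous bleeds, it does not read as a change.

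A spontaneous-only count can never exceed an all-bleed count. With window and threshold held fixed, the restriction can therefore only move joints into the resolved category, never out of it. The rule for new joints is the same in both documents, so nothing offsets this. The net change in number of target joints is shifted toward improvement by an amount that depends on how many joint bleeds are traumatic.

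**Working it through.** **1. The SAP's own figure.** Pro-rating the protocol limit to the study window gives 2 × 6/12 = 1 bleed. Both rules correspond to 2 bleeds per year. The threshold is reproduced exactly.

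**2. Bleed type, by example.** Take one pre-existing target joint with no bleeds in the 6 months before baseline and, on study, 0 spontaneous and 3 traumatic bleeds.

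- Protocol 8.2.3: 0 + 3 = 3 > 2, not resolved. End-of-study count 1 + 0 − 0 = 1.
- SAP 4.1.1.3: 0 ≤ 1, resolved. End-of-study count 1 + 0 − 1 = 0.
- All bleeds, 6-month threshold of 1: 3 > 1, not resolved. Count 1.

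**3. Size, with the 6-month window held fixed.** Inputs: threshold 1 and window 6 months (SAP 4.1.1.3). The on-study bleed rate r per joint per year and the spontaneous share s are assumptions, because the documents give neither. With Poisson bleeding at a constant rate, the mean count in 6 months is m = r × s / 2 for the SAP rule and m = r / 2 when all bleeds count. The chance of being called resolved is P(X ≤ 1) = e^(−m)(1 + m).

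For s = 0.5:

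- r = 3: SAP m = 0.75, e^(−0.75) × 1.75 = 0.83. All bleeds m = 1.5, e^(−1.5) × 2.5 = 0.56.
- r = 6: SAP m = 1.5, giving 0.56. All bleeds m = 3, e^(−3) × 4 = 0.20.

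Over a range of shares, using the same formula:

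| r per year | SAP, s = 0.3 | SAP, s = 0.5 | SAP, s = 0.7 | All bleeds (also SAP, s = 1) |
|---|---|---|---|---|
| 2 | 0.96 | 0.91 | 0.84 | 0.74 |
| 3 | 0.92 | 0.83 | 0.72 | 0.56 |
| 4 | 0.88 | 0.74 | 0.59 | 0.41 |
| 6 | 0.77 | 0.56 | 0.38 | 0.20 |

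**4. The window, kept separate.** With all bleeds spontaneous, compare P(X ≤ 1) at mean r/2 (6 months) with P(X ≤ 2) at mean r (12 months): 0.91 v 0.92 at 1/year, 0.56 v 0.42 at 3/year, 0.20 v 0.06 at 6/year. The two are equal at about 1.23/year. Below that the 6-month rule is marginally stricter; above it, easier to meet. This part comes from the disclosed window and is not counted in step 3.

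**5. Short follow-up.** The SAP does not say how its 6-month rule applies to a participant followed for about 4 months (122 days). If the threshold of 1 were kept, one bleed would annualise to 365.25/122 = 2.99 per year against the intended 2. At 4 spontaneous bleeds/year, P(X ≤ 1) would rise from 0.41 to 0.61. Pro-rating to 122 days gives 2 × 122/365.25 = 0.67, so no whole-number threshold matches.

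**The case against.** The strongest defence is that the SAP is open about what it does. It labels the definition as modified, says it differs from ISTH, gives the reason and prints the word spontaneous in the rule. The protocol's resolution sentence directly follows one about spontaneous bleeds and could be shorthand. Both documents cite the same outside definition, which cannot be consulted here, so which of them renders it correctly is open. Using spontaneous bleeds for both gaining and losing status is also internally consistent. All of this stands as a reason to allow either repair. It does not remove the conflict, because the two texts differ as written and the SAP says that nothing changed.

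A reader might infer more than the documents support:

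- **That the SAP's count is looser.** It is not; step 1 shows the same annual rate. A joint with no bleeds in the 6 months before baseline and 2 spontaneous bleeds on study is resolved under the protocol (2 in 12 months) but not under the SAP. The shorter window follows from the design: "All participants will receive treatment for a total of 6 months".
- **That only the SAP resolves joints that still bleed.** The protocol rule itself tolerates up to 2 bleeds.
- **That the gap between 3 bleeds to gain status and fewer to lose it is the SAP's doing.** The onset threshold is the protocol's own.
- **That the effect is 83% against 42%, or 56% against 6%.** Those contrasts set a 6-month spontaneous rule against a 12-month all-bleed rule, so they mix the disclosed window with bleed type.
- **That the SAP applies a threshold of 1 to 4-month participants.** It does not address them. This is a gap, not a stated rule.

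**Conclusion.** The point holds for bleed type. SAP 4.1.1.3 resolves target joints on spontaneous bleeds only, protocol 8.2.3 does not, and the SAP declares no change. A joint with repeated traumatic bleeds on study would be reported as resolved and subtracted from the end-of-study number.

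The size depends on the traumatic share. At one half, the restriction raises the chance of being called resolved by about 27 percentage points at 3 bleeds/year (83 − 56) and 36 points at 6/year (56 − 20). With no traumatic bleeds it raises it by nothing. These figures illustrate the mechanism under Poisson bleeding and assumed rates; they do not predict the trial's result.

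The consequence is limited. This is a descriptive secondary endpoint in about 20–25 participants, with no hypothesis test. SAP 4.3.2.2 reports pre-existing, new, resolved and end-of-study joints separately with a shift table, so the net figure does not stand alone. The primary endpoint does not use resolved joints, and the risk score uses joints at baseline.

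**What to change.** Keep the pro-rated threshold but count every bleed into the joint: resolved means no more than 1 bleed of any cause in 6 months. Report the spontaneous-only count as a sensitivity analysis.

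Alternatively, if the spontaneous-only rule is intended, list and justify it in SAP 4.7, reconcile the SAP's description of the source rule with protocol 8.2.3, and report the all-bleed count beside it.

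Under either option, do not classify joints as resolved in participants followed for less than the 6-month window; list them separately.

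The cost is SAP wording and one extra count. Protocol 8.2.1 already has the diary record cause, type and location of every bleed, treated or not, and SAP 4.1.1.3 already tracks bleeds by site. The downside for the sponsor is that fewer joints will be reported as resolved.
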